Our preliminary data suggest that a global, underlying mechanism of accelerated sarcopenia is an increase in anabolic resistance associated with a reduction in amino acid transport. With this application we will examine how amino acid transport is impacted by conditions accelerating sarcopenia and identify factors that control it.

In Specific Aim 1 we will determine if a well-known chronic accelerator of sarcopenia, T2DM, reduces the sensitivity of amino acid transport to increasing doses of exogenous amino acids. In Specific Aim 2 we propose that short-term bed rest inactivity will reduce the sensitivity of amino acid transport to exogenous amino acids and that T2DM will worsen this negative adaptation. Upstream regulatory pathways will be explored also in this aim to identify promising therapeutic targets for interventions.

Innovation

The research we propose is innovative, in our opinion, for at least three major reasons:

1. Conceptual Innovation. Our proposed studies will explore for the first time the potential global role of amino acid transport in conditions that accelerate sarcopenia chronically and acutely. By using a well described and common model of accelerated sarcopenia, T2DM, this research may also rapidly yield practical innovation that could be rapidly translated in the clinical setting.

2. Methodological Innovation. Innovation also stems from our novel integrative and interdisciplinary translational approach that combines state of the art and novel methodologies to determine amino acid transporter expression and function and their upstream regulation. These methodologies include: a 3-pool model tracer methodology to measure amino acid trafficking across vascular and intracellular compartments²⁰; molecular techniques to measure regulation of muscle protein synthesis and amino acid transport^{26,27}; and near infrared spectroscopy (NIRS) to determine the role of endothelial function and microvascular muscle perfusion^{86,87}. Inactivity is a well-established means to induce muscle atrophy. Bed Rest inactivity also reduce amino acid transport and transporter expression and leads to anabolic resistance²². In this application, we will *innovatively use Bed Rest as a tool to modify the response of amino acid transport and transporter expression* with the purpose of testing our hypotheses and identifying new therapeutic targets.

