All study data will be collected in REDCap by the research team. Paper data flow sheets or case report forms will be stored in locked file cabinets in a secure area of the PI's recruitment office. Interim data will be reviewed by the PI. Any appearance of a Conflict of Interest by the research team will be avoided by the periodic monitoring by UTMB's Conflict of Interest Committee. The subjects' right to confidentiality will be protected at all times and no subject will be identified by name in any publication that results from this research.

13. Potential Benefits:

The only potential benefits for the participation in this protocol are related to the knowledge of the results of the screening tests that will be released to the volunteer. The knowledge collected from the present studies may be of benefit to society, as these studies will help develop the scientific basis for designing treatments for reducing loss in muscle mass and function in older subjects with T2DM.

Importance of the Knowledge to be Gained. These studies will allow us to identify the biological mechanisms by T2DM accelerate sarcopenia in older individuals. Since T2DM is quite common in older adults and increase the risk of physical dependence, the knowledge to be gained will be very important to develop interventions to maintain independence in older adults.

13. Statistical Analysis:

Primary outcome variables will be measures of amino acid transport. All other variables will be treated as secondary outcomes. We will first compute the basal-to-acute treatment change for each variable in each subject. Experiment to test Aim 1 is designed using a 2×2 factorial approach with no repeated measures (see Table 1). A standard 2×2 ANOVA model will be used to test the main effects, treatment by group interactions, and contrasts of interest, particularly the interaction effect of EAA dose (Aim 1) on challenges to the metabolism by T2DM.

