Experiment for Aim 2 is designed using a 2×2 factorial approach with repeated measures across time (see Table 2). We will then use a standard repeated measures 2×2 ANOVA model to test the main effects, treatment by group interactions, and contrasts of interest, particularly the interaction effect of amino acid dose (Aim 1)/exercise (Aim 2) on the effect of bed rest. For each variable we will also test if there are basal differences between groups using one way ANOVA. If basal differences are found, we will then use the basal values as covariates. Factors such as age, sex, and BMI will also be considered as covariates. The same analytic plan will be used for secondary outcome variables, and the results will be used for the overall interpretation of our study. To further elucidate potentially important mechanistic relationships between the primary and secondary outcomes, along with their relationship to demographic characteristics such as sex, we will also use multiple regression models and other techniques, such as principal components analysis. Differences will be considered significant at $p<0.05$. Post-hoc testing will be carried out using the Tukey-Kramer test. All calculations will be conducted in SAS (version 9.2 or later; SAS Institute Inc., Cary, NC). As necessary, responses will be transformed to assure that model assumptions of normality and constant group variance are met. Results will be presented as mean \pm SD.

Table 2. Groups for Aim 2. Healthy and T2DM older adults will be randomized into two physical therapy groups: standard of care (Control) and Exercise. In all groups we will measure the effect of 7 g of EAA before and after 5 days of bed-rest, as described in Aim 1.

*same group randomized to 7 g of EAA in Experiment 2.

GROUP	PHYSICAL THERAPY	
	Control	Exercise
Control	BR-C7*	BR-ExC7
T2DM	BR-D7*	BR-ExD7

protein turnover and amino acid transport in bed rest and T2DM, we will balance groups by sex. In *Table 3* we report the expected differences as original or log transformed units, the SD, the calculated n/group and the n/group including subjects to offset the expected attrition of 12%.

Table 3. Sample size (n) per group, based on the primary outcome, to detect the expected smallest differences between groups (Δ_{min}) given the measured standard deviation (SD) of the difference, alpha=0.05 and beta=0.8. n= subjects/group, n+ = n/group including expected attrition rate.

Outcome Variable	Δ_{min}	SD	n	n+

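### The primary outcome is an unnamed, unranked set of amino acid transport measures with no error control across them, and Table 3 does not identify the lead measure

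*Combined protocol and SAP*

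**What the plan says.** **Primary outcome.** Section 13, Statistical Analysis: "Primary outcome variables will be measures of amino acid transport". It continues: "All other variables will be treated as secondary outcomes". No transporter, tracer, rate or lead measure is named there.

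**Candidates.** Section 4, Metabolic Experiment, says that the procedure measures both the expression and the function of amino acid transporters. It lists transport rates through LAT1 (phenylalanine and leucine tracers), SNAT2 (glycine) and PAT1 (glycine).

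**Testing.** Main effects, interactions and contrasts are tested for each variable at 0.05. The section stresses one interaction for Aim 1 ("particularly the interaction effect of EAA dose (Aim 1) on challenges to the metabolism by T2DM") and another for the repeated-measures model ("particularly the interaction effect of amino acid dose (Aim 1)/exercise (Aim 2) on the effect of bed rest"), but calls neither primary. On multiplicity it says only: "Post-hoc testing will be carried out using the Tukey-Kramer test".

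**Sample size.** The Table 3 caption ties the group sizes to the primary outcome, in the singular. The Sample Size and Power Calculation paragraph speaks of primary endpoints, in the plural, under the planned ANOVA. The table has two rows:
- Amino acid transporter expression: difference 0.52, SD 0.29, n 6, n with attrition 8.
- Leg Lean Mass: difference 0.40, SD 0.20, n 3, n with attrition 8.

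**The concern.** The plan separates primary from secondary outcomes and sizes the study on the primary, so the label has to point at something definite. Here it points at a class. Nothing in the written rules stops a result below 0.05 on any one member from being presented as the primary finding, and the chance of at least one such result under the null exceeds 5%.

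Two features of the protocol make a set left open more exposed to selection after the data are seen. If the femoral catheter cannot be placed, parameters that need that sample are not measured, so the available measures may differ between subjects (section 4). The principal investigator also carries out a quarterly interim data analysis (section 11).

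Table 3 would be the natural place to find the lead measure, but it does not supply one. Its transport-related row could be any transporter, and its other row is not a transport measure.

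**Working it through.** **1. Reproduce Table 3, row 1.** Inputs: difference 0.52, SD 0.29, alpha 0.05 (taken as two-sided), power 80% (the table prints this as beta = 0.8).
- Standardised difference: 0.52/0.29 = 1.793.
- For a pairwise contrast in a four-cell ANOVA, the error df are 4n − 4 and the noncentrality is 1.793 × √(n/2).
- At n = 6: df 20, noncentrality 3.106, critical t 2.086, power 84.0%. At n = 5, power is 75.9%. The smallest adequate n is therefore 6, as printed.
- This treats 0.29 as the per-group SD, although the caption calls it the SD of the difference. The alternative, a per-group SD of 0.29/√2 in a two-group t-test, gives n = 4, so the per-group reading fits the table better.
- Attrition: 6/0.88 = 6.8, which rounds up to 7. The printed 8 matches the Table 1 group size. With 8 enrolled, about 8 × 0.88 = 7 complete.

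**2. Error across measures.** The number of measures k is not given, so it is assumed. Two stands for expression and function, and three for one measure per named transporter. Six stands for expression and function of each transporter. Each measure is tested once, on one contrast. For independent tests the rate is 1 − 0.95^k. For correlated tests it comes from simulation of equicorrelated two-sided normal tests.

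| k | correlation 0 | 0.5 | 0.7 |
|---|---|---|---|
| 2 | 9.8% | 9.0% | 8.3% |
| 3 | 14.3% | 12.6% | 10.9% |
| 6 | 26.5% | 20.7% | 16.4% |

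The same exercise with the Aim 1 interaction t-test (8 per cell, 28 df) gave nearly the same values, for example 14.1%, 12.7% and 11.0% for k = 3. Testing several effects per measure would raise all of these.

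**3. Does Tukey-Kramer cover this?** No. It adjusts pairwise comparisons among groups within one variable. It does not adjust across variables.

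**4. Power cost of adjusting.** Same contrast and ANOVA error term as in step 1, with each measure tested at 0.05/k (Bonferroni).

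| Completers per group | k = 1 | k = 2 | k = 3 |
|---|---|---|---|
| 8 (df 28, noncentrality 3.586) | 93.3% | 88.1% | 84.3% |
| 7 (df 24, noncentrality 3.355) | 89.6% | 82.5% | 77.6% |

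Holm rejects whenever Bonferroni does, so these are lower bounds for Holm.

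**5. Aim 1 interaction, for information.** Assume that the difference of differences is 0.52. The standard error is 0.29 × √(4/n). Unadjusted power is 68.7% at 8 per group and 62.4% at 7. No Aim 2 figure is offered, because it depends on the SD of within-person change, which the documents do not give.

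**The case against.** **Table 3 already names the lead.** The caption and the sample-size paragraph both say that the sizing is for the primary outcome or endpoints. Expression is the only transport-related row. The ordinary reading is therefore that transporter expression is a primary measure, and this stands. A reader might go further and infer that Table 3 sizes no primary measure at all, because the Innovation text speaks of bed rest as a tool to "modify the response of amino acid transport and transporter expression", as if these were two things. That phrase is background and defines no endpoint, so it does not support the inference. But the ordinary reading does not say which transporter, does not rank expression against the transport rates, and does not explain Leg Lean Mass.

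**Strict control is excessive in a small mechanistic study.** This stands in part. The plan states no rule that one positive measure is enough, and it speaks of using the results for overall interpretation. Naming the measures in advance is the stronger request. Holm is needed only if several stay primary.

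**Six measures is not established.** This stands. SNAT2 and PAT1 share one glycine tracer, and nothing says that their rates are separated. A reader might quote the 26% figure as the trial's error rate. The documents do not support that, and the six-measure row is only an illustrative upper case.

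**The measures may be listed elsewhere.** The Metabolic Experiment section refers to an Analytical Methods section that is not in the text supplied, so this cannot be checked. A list alone would neither choose a lead nor control error.

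**Conclusion.** The point holds. The plan names no lead transport measure and gives no control of error across the primary set. On the assumed counts of two or three measures, each tested once, the chance of at least one false-positive primary result is about 8–10% or 11–14% instead of 5%. These figures rest on the assumed count, on equal correlation between 0 and 0.7, and on one contrast per measure. Confidence is high on the missing error control and on the conflict over Leg Lean Mass. It is lower on the exact size, because the count is unknown.

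The findings on Table 3 are limited to three: row 1's transporter is not identified, no transport rate is sized, and Leg Lean Mass sits in a table based on the primary outcome although section 13 makes non-transport variables secondary. A reader might also infer that the study is too small. This point does not show that: with one named primary measure no adjustment across measures is needed, and row 1's n = 6 stands if 0.52 and 0.29 apply to that measure.

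**What to change.** Before analysis, do one of the following:
- **Preferred, for simplicity:** name one primary transport measure and make the others secondary. The choice is the sponsor's. The cost is that a real effect on another measure counts only as secondary evidence.
- **Alternative:** list the primary measures and apply Holm across them. The cost is power on a given measure. At 7 completers per group, the worst case falls from about 90% to about 82% for two measures or 78% for three.

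In either case:
- State one primary contrast per aim. For Aim 2 the sponsor must choose, because section 13 stresses exercise on the bed-rest effect while the Background hypothesis is that "T2DM will worsen this negative adaptation".
- In Table 3, state which transporter-expression variable gave 0.52 and 0.29, and whether it is the primary measure. Reconcile the status of Leg Lean Mass with section 13.
- Optionally, report the Aim 1 interaction power beside Table 3, with its assumption.

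The work is analysis-plan wording plus the sponsor's choice of measure and contrasts. It needs no additional subjects or procedures.

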Screening: After carefully explaining procedures and risks, informed consent will be obtained from all subjects. Eligibility will be assessed with clinical history, physical exam, questionnaires, functional testing, DEXA scan and a number of laboratory tests including blood count, metabolic panel, uric acid, lipid profile, coagulation panel, hemoglobin A1c, Hepatitis B and C, HIV test, urinalysis and urine toxicology drug screening. The subjects will arrive fasting for their screening visits for blood measures. An OGTT will be performed, which may involve the use of U-¹³C glucose tracer to better characterize glucose metabolism. Habitual physical activity will be measured using both StepWatch Activity Monitors (SAM) and pedometers for 1 week during the screening process. Rescreening of subjects who did not meet inclusion criteria for reasons that may resolve over time as determined by the investigator is allowed (e.g. dehydration, acute infections, medications, etc.). Subjects will be rescreened within 3 months and only 1 rescreen will be allowed per subject.

4. Study Design. Subjects will undergo a two acute metabolic experiments, one prior to and one immediately following the completion of 5 days of Bed Rest, in which we will test the effects of 7 or 21 g of EAA in older healthy and T2DM patients. The study will last a total of 7 consecutive days, including the bed rest staying and the following rehabilitation. Note that the rehabilitation period could be prolonged according to the physical therapist evaluation. If this will be the case, the physical therapist will provide extra rehabilitation treatment as usually occur during hospital provider.

[figure not shown]

Figure 1. Metabolic Study design with approximate timing.

- Provide standardized meals (see above).
- Hold vasodilators, monitor blood pressure, and manage hypertension with other medications if necessary ^{43,75,87}.

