2) Metabolic Experiment. The experimental procedure is designed to measure skeletal muscle amino acid transporter expression and function, whole body and muscle amino acid kinetics, muscle protein synthesis and proteolysis is depicted in *Figure 1*. The subjects will be studied in the post-absorptive state, after an overnight stay in the ITS-CRC. After admission, subjects will be given dinner at approximately 18:00 and a snack at approximately 21:00, after which they will be allowed only water ad libitum. At ~06:30 we will measure body composition by DEXA. At approximately 07:00 we will insert: an antecubital forearm venous catheter for systemic infusions; a retrograde venous catheter in the opposite hand placed in a heating pad for arterialized blood draws. At approximately 0900, we will place if possible a 3 French/ 8 cm or 4 French/ 12 cm pediatric central catheter in the femoral vein for blood draws. If not possible the femoral catheter will not be placed and the metabolic parameters that need a femoral venous blood sample will not be measured. Subsequently, we will start a primed-continuous infusion of L-[ring-¹³C₆]-phenylalanine, L-[5,5,5-²H₃]-leucine, and [1-¹³C]-glycine to measure muscle

1) Run-In: Subjects will report to the Institute for Translational Sciences Clinical Research Center (ITS-CRC) the day prior to the experiment, in this occasion we will:

- Follow current institutional COVID-19 testing policy. If positive the subject will be referred to own PCP. If negative we will:
 - Admit subjects to the ITS-CRC.
 - Draw safety labs including blood count, metabolic panel, coagulation panel, urinalysis. Additional labs may be ordered by the study clinical provider, as clinically appropriate, if changes in the medical history have occurred between screening and admission.

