protein turnover as well as the amino acid transport rates through LAT1 (Phe, Leu), SNAT2 (Gly), and PAT1 (Gly)^{55,93}. To reach the intracellular space, amino acids have to first be transported across the endothelium and then across the muscle fiber membrane⁶⁶. To reduce risks we will use arterialized blood samples, rather than arterial blood, to measure arterial amino acid concentrations and enrichments. This method has been previously validated for amino acid and other metabolite concentrations⁸, and we have preliminary data indicating that it is also valid for amino acid enrichments. Whenever possible we will also perform a Flow Mediated Dilation test to detect endothelial function using Doppler Ultrasound and Near Infrared Spectroscopy. After an approximately 4-hr baseline period, subjects will ingest the assigned amino acid mixture, as a bolus. The mixture will contain EAA in the pattern found in animal protein²² and will be enriched with L-[ring-¹³C₆]-phenylalanine, L-[5,5,5-²H₃]-leucine to maintain the isotopic steady state²² (labeled glycine will not be added because it is not included in the oral mixture). Large vessel blood flow will be measured by Doppler^{86,87}. Microvascular nutritive flow is emerging as a potential regulator of muscle amino acid and protein metabolism⁸⁵⁻⁸⁷. Thus, we will measure it in the basal state (see above) and after amino acid ingestion using Near Infrared Spectroscopy (NIRS) and measuring blood flow using Doppler Ultrasound. Frequent blood samples will be collected during the last hour of the basal period and the first and third hour of the amino acid period to measure amino acid concentrations and enrichments, glucose, insulin, cytokines and endothelin-1. T2DM is characterized by hyperglycemia, hyperinsulinemia, inflammation and endothelial dysfunction, which may have an impact on muscle protein metabolism^{69,86}. Additional serum samples will also be collected and stored for future analyses (e.g. other hormonal assays, proteomics, metabolomics). Two muscle biopsies will be taken in each period to measure all pertinent amino acid and protein kinetic parameters, cross-sectional area, cell signaling, novel regulatory pathways, and gene expression (see Analytical Methods). A portion of the biopsies will be collected for immunohistochemistry. A third incision may be made should the need arise. At the end of the experiment catheters will be removed and subjects will be given a meal. The metabolic study will take approximately 8 hours.

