
3) Physical Inactivity (Bed Rest). After the Metabolic Experiment is completed, subjects will start bed rest inactivity. UTMB has a long tradition of safely performing bed rest studies of any length (from a few days to up to 90 days) in adults of all ages, including seniors (see for example refs.^{22,31,32,70,77}). The UTMB ITS-CRC is equipped with specialized rooms for bed rest studies, which include CCTV cameras for continual monitoring and recording of subject to ensure that bed rest is effectively maintained throughout the experimental period. Recordings may be retained for a period not to exceed 45 days for review and will then be erased. Highly trained nursing staff and other patient care personnel is available at all times. The following standard procedures will be implemented for subject safety and comfort:

- A slight bed-back elevation will be permitted and subjects may raise their shoulders with two pillows.
- Periodic change of position in bed to alleviate positional discomfort and to eat.
- Serial compression devices (SCDs) and compression stockings will be worn to decrease DVT risk.
- Low molecular weight heparin (day 1-4)
- Standard of care in-bed physical therapy for bedridden patients involving passive range of motion of the lower extremity major joints.
- In-bed bathing, hygiene activities and diuresis.
- Bedside commode allowed for bowel movements.

The total energy content of the subjects' diet during bed rest will be reduced to account for inactivity. However, the protein content will remain at the pre-bed rest RDA level (0.8 g/kg/day)^{32,37}. T2DM patients will continue their anti-hyperglycemic treatment with glinides and/or short acting insulin, adjusted as necessary. Blood glucose will be continuously monitored during bed rest using a device called Continuous Glucose Monitor (CGM).

4) End of Bed Rest. On day 5 of bed rest body composition by DEXA, Metabolic Experiment and functional tests will be repeated. After the tests, subjects will be allowed to de-ambulate with staff help.

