All unanticipated, serious, fatal and/or life-threatening adverse events will be reported to the IRB within 24h of occurrence. The IRB and the PI will be responsible for determining whether modifications to the protocol and consent form are required. If a determination is made that participants are found to be exposed to excessive risks in relation to anticipated benefits, the study will be immediately suspended. Studies will not resume until modifications are made that are deemed to result in an acceptable risk/benefit ratio by the PI and the IRB. Aggregate reports of adverse events will be prepared as mandated and forwarded to the IRB and ITS-CRC for review.

Plan for Adverse Event Reporting. The PI will be responsible for evaluating each adverse event and determining attribution as well as the impact on the risk/benefit ratio, using the following Grading and Attribution criteria:

Mild – transient laboratory test alterations that do not suggest injury; discomfort noted but no disruption of daily activities; no therapy, or only symptomatic therapy required.

Moderate – Laboratory test alterations indicating injury without long-term risk, discomfort sufficient to modify normal daily activity, specific therapy required (i.e., more than symptomatic).

Serious – laboratory tests indicating a serious health threat or permanent injury, incapacity, inability to work, or to perform normal daily activity, hospitalization required or prolonged, emergency treatment required, life-threatening events, death.

The attribution scale assesses the relation of the event to the study procedures. [name] will judge whether an adverse event is: 1) *not related*; 2) *possibly related*; 3) *probably related*; or 4) *definitely related to the study interventions*.

Table 1. Groups for Aim 1. Older adults with T2DM and healthy controls will be randomized to two groups (n=8/group) receiving 7 g or 21 g of EAA.

	Essential Amino Acid Dose	
	7 g	21 g
Control	C7	C21
T2DM	D7	D21

12. Procedures to Maintain Confidentiality:

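### Leg lean mass has no basal-to-acute change, and the Aim 2 model as defined by Table 2 leaves 21 g bed-rest subjects out of analyses of pre-drink outcomes that could include them

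*Combined protocol and SAP*

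**What the plan says.** **Response variable.** Section 13, Statistical Analysis: "We will first compute the basal-to-acute treatment change for each variable in each subject". No exception is given. After the Aim 2 model is described, the section adds: "The same analytic plan will be used for secondary outcome variables".

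**Timing.** Section 4, Metabolic Experiment: "At ~06:30 we will measure body composition by DEXA". The drink comes much later: "After an approximately 4-hr baseline period, subjects will ingest the assigned amino acid mixture, as a bolus". Section 4, End of Bed Rest: "On day 5 of bed rest body composition by DEXA, Metabolic Experiment and functional tests will be repeated". The order of the functional tests and the second drink is not stated.

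**Who has bed rest.** Section 4 opens with two experiments, one on each side of five days of bed rest, "in which we will test the effects of 7 or 21 g of EAA in older healthy and T2DM patients". Table 1 gives the dose allocation: healthy and T2DM subjects "will be randomized to two groups (n=8/group) receiving 7 g or 21 g of EAA".

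**Who is in the Aim 2 model.** Table 2 crosses diagnosis with physical therapy. Its note reads "In all groups we will measure the effect of 7 g of EAA before and after 5 days of bed-rest", and its four cells are BR-C7, BR-ExC7, BR-D7 and BR-ExD7. It has no 21 g cell. The text on the repeated-measures model nevertheless lists, among the contrasts of interest, the interaction of dose (assigned to Aim 1) or exercise (assigned to Aim 2) with the effect of bed rest.

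**The concern.** There are two linked gaps.

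First, the prescribed response does not exist for an outcome with one reading per experiment, taken before the drink. Leg lean mass is the clear case. Basal transporter expression and basal kinetics are similar: they are the starting points of the basal-to-acute change, so their own change over bed rest is not defined as a response anywhere.

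Second, on the day of measurement the assigned dose has not yet been taken. Dose can reach the day-5 value only through the single drink at the first experiment. The 21 g subjects therefore carry information on what bed rest does to these outcomes, and on whether T2DM makes it worse. Under Table 2 they are not in the model.

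At stake is precision in a small trial. Subjects who accept the same bed rest and repeat procedures would contribute nothing to the bed-rest comparison for these outcomes.

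**Working it through.** **Plan's own figures (Table 3).** Two-sided alpha 0.05 and power 0.80 are assumed; the table prints the latter as beta.
- The normal formula n = 2(1.96 + 0.84)² × (SD/Δ)² gives 15.7 × (0.29/0.52)² = 4.9, so 5, for transporter expression. With four-group ANOVA error degrees of freedom it is 6, the stated value.
- For leg lean mass, 15.7 × (0.20/0.40)² = 3.9, so 4, against a stated 3. The two-sample t gives 6.
- Both rows are then set to 8 per group with attrition. I use 8 per cell, as in Table 1.

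**Set-up.** With two time points and complete data, the repeated-measures model is equivalent to a linear model for each subject's bed-rest change. The SE of a difference between two groups of n is SD × √(2/n). Results are in units of the SD of the change. Detectable differences use the noncentral t, two-sided 0.05, 80% power and 2n − 2 degrees of freedom.

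**Reading A: separate exercise groups of 8.** Each diagnosis has 8 standard-care 7 g and 8 exercise 7 g subjects. Adding C21 or D21 makes 24.

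| Contrast in bed-rest change | Table 2 model | With 21 g subjects | Planned SE too large by |
|---|---|---|---|
| T2DM − control, pooled over therapy | √(2/16) = 0.354 | √(2/24) = 0.289 | 22% |
| T2DM − control, therapy cells weighted equally | 0.354 | ½√(2/16 + 2/8) = 0.306 | 15% |
| T2DM − control, standard care only | √(2/8) = 0.500 | √(2/16) = 0.354 | 41% |
| Exercise − standard care, dose × time fitted | √(1/16 + 1/16) = 0.354 | 0.354 | 0% |
| Exercise − standard care, no dose term | 0.354 | √(1/32 + 1/16) = 0.306 | 15% |

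The first row is the same with or without dose × time, because dose and therapy are balanced across diagnosis (8/8/8 in each). In the exercise rows, fitting dose × time leaves the 7 g standard-care subjects as the only comparator, so the gain vanishes.

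**Detectable difference and power.**
- Pooled over therapy, 16 v 16 to 24 v 24: 1.02 to 0.83 SD. Power goes from 59% to 77% at 0.8 SD, and from 78% to 92% at 1 SD.
- In leg lean mass units, taking Table 3's 0.20 as the SD of the change: 1.02 × 0.20 = 0.20 to 0.83 × 0.20 = 0.17.
- Standard care only, 8 v 8 to 16 v 16: 1.51 to 1.02 SD; power at 1 SD 46% to 78%.
- With 7 per cell after attrition, the SE ratios do not change.

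**Reading B: the 7 g groups are split about 4/4.** The Group Randomization paragraph can be read this way. Pooled over therapy, T2DM − control goes from 8 v 8 to 16 v 16, an excess of 41%. The standard-care change within one diagnosis goes from 4 to 12 subjects, an excess of √3 − 1 = 73%. Exercise with dose × time still gains nothing (0.500 either way).

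**The case against.** **The 21 g subjects may not be excluded.** The repeated-measures text names dose on the effect of bed rest, which can be tested only with C21 and D21. Extended to secondary outcomes, that would give a 16 v 16 standard-care comparison. This stands in part. A reader might infer that the plan discards these subjects, but the documents do not go that far. They also do not supply the model: the Aim 2 design is a 2×2 tied to Table 2, with no dose factor and no 21 g cell.

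**A flat 41% would be wrong.** A reader might apply √2 to every bed-rest standard error. Under Reading A it belongs only to the standard-care simple effect. The planned diagnosis × time test already uses 16 v 16. This stands.

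**Lean mass is not shown to be underpowered.** At Table 3's own difference, 0.40/0.20 = 2 SD, even 8 v 8 has 96% power. This stands. The 0.8 and 1 SD targets are illustrations, not the plan's.

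**Aim 2 is about the response to the drink.** Section 2 frames it as sensitivity of transport to exogenous amino acids. Section 13 makes everything except transport secondary and uses basal values as checks and covariates. This stands and limits the importance of the point.

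**Dose may not be irrelevant at day 5.** The documents do not say that it is. One earlier drink precedes the day-5 values, and functional tests are not shown to precede the second drink. A dose main effect would not detect carry-over on the change; dose × time would. With that term the diagnosis gain survives.

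**Conclusion.** The point holds in a limited form. The prescribed response cannot be computed for leg lean mass, and Section 13 does not say how the 21 g subjects' bed-rest data on pre-drink outcomes are used. If they stay out, the SE of the T2DM-control difference in bed-rest change is 22% larger than needed when pooled over therapy, or 15% if therapy cells are weighted equally. It is 41% larger only for the standard-care comparison. That figure applies to the standard-care bed-rest change itself if dose does not affect the change, and to its T2DM-control difference when averaged over dose. Exercise contrasts gain nothing once dose × time is fitted.

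These sizes assume 8 per cell, separate exercise groups, a common SD, standard-care therapy for the 21 g subjects, and (for the pooled figure) no diagnosis × therapy or diagnosis × dose interaction on the change. Splitting the 7 g groups 4/4 would make them larger. The documents do not support reading this as a failure of Aim 2's main question or as a lack of power for lean mass. It is a cheap improvement for secondary and supportive outcomes.

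**What to change.** In Section 13:

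1. Limit the basal-to-acute step to variables measured both before and after the drink. For outcomes measured before it (leg lean mass, basal transporter expression, basal kinetics), define the response as the pre- to post-bed-rest change.
2. Analyse that change with C21 and D21 included as standard care, in a model with diagnosis, therapy and dose, each crossed with time. State how therapy groups are weighted in the T2DM-control contrast.
3. Treat functional tests this way only if they are confirmed to precede the second drink. Otherwise keep dose × time in their model whatever it shows.
4. Keep responses to the drink in the 7 g groups of Table 2.
5. State whether the exercise groups are recruited separately or split from the 7 g groups, because the sizes above depend on it.

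The cost is wording and one extra model term; the planned measurements already supply the data. The small downside is that the standard-care bed-rest mean is then averaged over the two dose groups.
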